### 7.4.1 Clinical laboratory abnormalities

Clinical laboratory results that are outside of the normal ranges will be considered AEs if deemed clinically significant by the Investigator.

An abnormal lab value should be deemed clinically significant if either of the following conditions is met:

- The abnormality suggests a disease and/or organ toxicity that is new or has worsened from baseline.
- The abnormality is of a degree that requires additional active management, e.g., change of dose, discontinuation of the drug, close observation, more frequent follow-up assessments, or further diagnostic investigation.

## 7.5 Secondary Malignancy

A secondary malignancy is a cancer caused by treatment for a previous malignancy (e.g., treatment with investigational agent/intervention, radiation, or chemotherapy). A secondary malignancy is not considered a metastasis of the initial neoplasm.

All secondary malignancies that occur following treatment with an agent under this protocol will be reported via CTEP-AERS. Three options are available to describe the event:

- Leukemia secondary to oncology chemotherapy (e.g., acute myelocytic leukemia [AML])
- Myelodysplastic syndrome (MDS)
- Treatment-related secondary malignancy

Any malignancy possibly related to cancer treatment (including AML/MDS) should also be reported via the routine reporting mechanisms outlined in each protocol.

## 7.6 Second Malignancy

A second malignancy is one unrelated to the treatment of a prior malignancy (and is **NOT** a metastasis from the initial malignancy). Second malignancies require **ONLY** routine adverse event reporting.

## **8.0 PHARMACEUTICAL INFORMATION**

### **8.1 Efudex (5-fluorouracil 5%)**

#### **8.1.1 Product description**

Efudex cream is a topical preparation, available in a 40 gm tube, containing the fluorinated pyrimidine 5-fluorouracil, an antineoplastic antimetabolite. 5% 5-fluororacil contains 5 grams of 5-fluororacil per 100 grams. Efudex Cream contains 5% fluorouracil in a vanishing cream base consisting of white petrolatum, stearyl alcohol, propylene glycol, polysorbate 60 and parabens (methyl and propyl). Chemically, fluorouracil is 5-fluoro-2,4(1H,3H)-pyrimidinedione. It is a white to practically white, crystalline powder which is sparingly soluble in water and slightly soluble in alcohol. One gram of fluorouracil is soluble in 100 mL of propylene glycol. The molecular weight of fluorouracil is 130.08 and the molecular formula is C4H3FN2O2.

#### **8.1.2 Storage**

Store at 25°C (77°F); excursions permitted to 15°C-30°C (59°F-86°F).

#### **8.1.3 Route of administration**

The agent will be administered per rectum. Participants will self-apply the medications with a syringe or their gloved fingers as described in [Section 5.1](#).

Refer to the approved package insert for complete prescribing and toxicity information.

### **8.2 Zyclara (imiquimod 2.5%)**

Zyclara was discontinued on this protocol as of version 5.0 due to product unavailability.

#### **8.2.1 Product description**

Imiquimod belongs to the chemical class of substances known as imidazoquinoline amines. Chemically, imiquimod is 1-(2-methylpropyl)-1H-imidazo[4,5-c]quinolin-4-amine. Imiquimod has a molecular formula of C14H16N4 and a molecular weight of 240.3. Imiquimod is available as a white to faintly yellow oil-in-water cream base consisting of isostearic acid, cetyl alcohol, stearyl alcohol, white petrolatum, polysorbate 60, sorbitan monostearate, glycerin, xanthan gum, purified water, benzyl alcohol, methylparaben, and propylparaben.

Imiquimod cream (Zyclara), 2.5% is available in 7.5 and 15 gm pump bottles, each gram of cream contains 25 mg of imiquimod. Pump bottles dispense 5.9 mg of imiquimod in 0.235 gm of cream per full actuation of the pump after priming. The 7.5 gm pump delivers no fewer than 28 full actuations and the 15 gm pump delivers no fewer than 56 full actuations.

#### **8.2.2 Storage**

Store at 25°C (77°F); excursions permitted to 15° to 30°C (59° to 86°F). Avoid freezing. Store ZYCLARA Cream pumps upright.

### 8.2.3 Route of administration

The agent will be administered per rectum. Participants will self-apply the medications with a syringe or their gloved-fingers as described in [Section 5.1](#).

Refer to the approved package insert for complete prescribing and toxicity information.

## 8.3 Study Agent Supply, Distribution and Accountability

Study agents will be supplied by the manufacturers.

### 8.3.1 Study agent acquisition

Participating sites are to refer to the study drug request form located on the AMC Operations Center web site ([www.AIDSCancer.org](http://www.AIDSCancer.org)).

### 8.3.2 Study agent accountability

For all study-supplied topical agents, the Investigator, or a responsible party designated by the Investigator, must maintain a careful record of the inventory and disposition of all drugs received using the NCI Investigational Agent Accountability Record Form (DARF), available on the CTEP home page (<http://ctep.cancer.gov>) or by calling the Pharmaceutical Management Branch at [contact]. The DARF documents the drug delivery date to the site, inventory at the site, use by each study participant, and disposal of the drug (if applicable). A site-specific accountability record, either manual or electronic, may be used if it includes all the information required on the DARF and if the paper printout is identical to the DARF. A separate DARF is required for each protocol using the same agent. The investigator will ensure that the drugs are used only in accordance with this protocol.

### 8.3.3 Study agent transfers

Agent may not be transferred from one subject to another subject, from one center to another center, or from one protocol to another protocol.

### 8.3.4 Study agent destruction

Agent returned by participants must be weighed prior to destruction and return must be documented in source documents.

Expired agent may be destroyed according to local policies. At the end of the study, unused agent may be destroyed according to local policy with written authorization from the AMC ODMC.

## **9.0    RESPONSE CRITERIA**

CTEP-registered advanced practice clinicians who are non-physician investigators (i.e., NP or PA) may perform toxicity and response assessment as allowed per local licensure.

### **9.1    Definition of Clinical Response (by Subject)**

- 9.1.1    Complete Response (CR): The absence of HSIL histology for all biopsies and the absence of HSIL cytology.
- 9.1.2    Partial Response (PR): 1) The regression of HSIL histology but HSIL cytology is present, or 2) Reduction in number of octants with HSIL.
- 9.1.3    No Response: The presence of HSIL histology with no change in the number of octants with HSIL with or without HSIL cytology.
- 9.1.4    Spontaneous Regression: The absence of HSIL histology and HSIL cytology following no treatment.

Please note that LSIL is treated the same as no SILs for the purpose of these definitions. For example, a participant with all biopsies showing LSIL and cytology showing LSIL would be considered a CR.

## **10.0 STATISTICAL CONSIDERATIONS**

### **10.1 Rate of Accrual**

This study is expected to accrue eight participants per month for a total of 118 participants (50 per arm for observation and 5FU arms and 18 to the imiquimod arm, which closed because of lack of drug availability). However, the rate of accrual has been approximately one participant per month from 2021-2023. With Version 8.0, the sample size has been reduced to 88 participants (35 per arm for observation and 5FU arms and 18 to the imiquimod arm).

### **10.2 Randomization**

The study will use a stratified, random permuted block randomization scheme with strata being sites. This approach ensures that arms are balanced within sites.

### **10.3 Sample Size Estimation**

The original sample size was based on the assumption that treatment of anal HSIL lesion with topical therapy (topical 5-fluorouracil 5%) will have a minimum CR rate of 40% as compared to a maximum regression rate of 10% in the observation arm. Due to the slow accrual rate, the sample size was reduced, and the revised sample size was decided by the expected accrual close date (01 July 2023). Thirty five participants per arm (or 70 in total for observation and 5FU arms) would be the revised sample size. Eighteen participants were accrued to the imiquimod arm prior to this arm being closed because of lack of drug availability. The comparison of imiquimod to observation is no longer sufficiently powered to test efficacy; comparisons to imiquimod will be considered exploratory.

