#### I. Scientific and Substantive Changes:

#	Section	Comments
1.	Synopsis 1.2 10.1 10.3 10.6.2	
The target accrual was updated from 118 participants to 88 participants due to feasibility concerns with the rate of accrual.
 
Sample size estimation was updated to include the following information:
 

• Due to the slow accrual rate, the sample size was reduced, and the revised sample size was decided by the expected accrual close date (01 July 2023). Thirty-five participants per arm (or 70 in total for observation and 5FU arms) would be the revised sample size.

 
Table 10-A was updated to reflect the updated sample size, <math>H_0</math> (Futility) Bound Z (P-value), <math>H_1</math> (Efficacy) Bound Z (P-value) and Overall <math>\beta</math> (1-power) Spent

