## 1.2 Study Rationale

Richel et al. (35) reported on 148 HIV-infected MSM with squamous intraepithelial lesions (SIL; 57% with HSIL) randomized to 4-month treatments with 2% 5-fluorouracil, 5% imiquimod, or monthly electrocautery. The response rate was 17%, 24%, and 39%, respectively in the intention to treat group with severe side effects reported as 27%, 43%, and 18%, respectively. Recurrence rates were 58%, 71%, and 68% at 72 weeks post-treatment. In the per protocol group with HSIL, the complete response rate was 21%, 21%, and 50% respectively. This is the first report comparing fluorouracil to imiquimod in a randomized study. While these data indicate that monthly ablation may be superior to either topical cream in the population studied, it may not be appropriate or be the best treatment for those with extensive anal HSIL. In addition, the treatment regimens are differently than what is commonly used for treatment in North America. Richel et al. studied one dose of 2% 5-fluorouracil applied twice weekly, which is lower than what we are proposing in this trial. Further, inserting either agent with suppositories may inadvertently bypass the anal mucosa thereby reducing efficacy. Richel et al. may have confirmed this in that they reported better efficacy of treatment to perianal lesions compared to intra-anal lesions. Our study proposes application of the agents directly to the anal mucosa.

We are proposing an arm with no treatment for up to 20 weeks. This group is necessary to clearly show the activity of these compounds. There are few data on the regression of anal HSIL in the absence of treatment. Fox et al. observed regression in one out of 25 participants randomized to placebo. The risk of progression for this duration of observation is very low, especially with interim anoscopy during the treatment period.

The imiquimod arm was closed as of protocol version 5.0 due to product unavailability.

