Rationale in the context of ANCHOR results: The absolute risk of cancer over the course of randomized therapy (24 weeks) was very low in both arms. There are ongoing randomized controlled trials of HPV therapeutic vaccines that randomize women with cervical HSIL to no treatment for a similar short period. We believe the risk is small and is lessened by interim anoscopic monitoring of participants with the option to remove the participant from the study for fear of imminent progression. Participants who appear at risk for progression to cancer are not enrolled into AMC-088. As of 19NOV2021, no cases of invasive cancer have developed in AMC-088.

Version 8.0 reduces the sample size from 118 to 88. The primary analysis is not changing.

The effect of this sample size change on statistical power is discussed in [Section 10.0](#). The motivation for the change is because of the slow accrual despite multiple strategies to increase enrollment. Enrollment closed as of 01JUL2023.

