#### 10.6.2 Futility and efficacy halting rules

An interim analysis is planned after 50% of the ITT population has completed assessment for the primary endpoint to assess the futility of achieving a significant result if the study continues and to potentially demonstrate efficacy before all participants are enrolled. For the comparing topical 5-fluorouracil 5% vs observation, group sequential methods will be used to compare efficacy endpoints preserving the overall one-sided significance level of 0.025 for each comparison. To assess superiority of a treatment arm in comparison to observation the Lan-DeMets stopping boundaries will be used. To assess futility, the O'Brien-Fleming futility boundaries will be used. The interim analyses will be reviewed by the AMC Data and Safety Monitoring Board (DSMB) by the 50% point.

**Table 10-A: Statistical test boundaries and associated operating characteristics for testing efficacy of 5-fluorouracil 5% vs. observation**

Analysis	Total Number (%) of Subjects*	$H_0$ (Futility) Bound Z (P-value)	$H_1$ (Efficacy) Bound Z (P-value)	Overall $\alpha$ Spent	Overall $\beta$ (1-power) Spent
1 (Interim)	35 (50%)	0.258 (0.398)	2.963 (0.002)	0.002	0.020
2 (Final)	70 (100%)	1.955 (0.025)	1.955 (0.025)	0.025	0.100

\*Total number of subjects equals the number in 5FU arm plus observation arm.

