### 10.7 Primary Analyses

The primary analysis population for efficacy and safety is an intent-to-treat (ITT) population, which consists of all participants who are randomized to 5-fluorouracil 5% or observation. The proportion of participants achieving complete response in the 5-fluorouracil 5%, and the proportion of participants with spontaneous regression in the observation arm will be calculated as the number achieving complete response or experiencing spontaneous regression through the primary endpoint visit (Week 20) divided by the number in the intent-to-treat population. For the treatment comparison (topical 5-

fluorouracil 5% vs. observation) the proportions will be compared across sites using stratified Mantel-Haenszel-Cochran tests at the one-sided 0.05 alpha level. This means that participants who drop out or do not provide evaluable data contribute to the analysis since they are included in the denominator, i.e., they are essentially treated as failures.

Since the imiquimod arm was stopped early, we will describe comparisons between imiquimod and observation using only the participants randomized to imiquimod and observation prior to closure of the imiquimod arm. As a secondary objective, imiquimod 2.5% and topical 5-fluorouracil 5% will be compared using a stratified Mantel-Haenszel-Cochran test at the two-sided 0.05 alpha level using participants randomized prior to the closure of the imiquimod arm.

The primary endpoint will include intra-anal HSIL present on cytology or histology. Perianal HSIL will be descriptively reported separately, as well as combined with the primary endpoint. In addition to the primary intent-to-treat analysis (which includes all randomized participants), we will perform a sensitivity analysis that treats participants who receive HSIL treatment other than randomized treatment (or observation participants that receive any treatment) prior to Week 20 as failures; participants who are lost to follow-up or inevaluable are also still treated as failures. We will also perform a per-protocol analysis using the subset of participants who were adherent to the protocol.

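### Table 10-A shows 90% power at 35 per arm, but at 40% vs 10%, the only effect size stated, its own bounds give about 85%

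*Combined protocol and SAP*

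**What the plan says.** Section 10.3 gives one pair of design rates. Treatment "will have a minimum CR rate of 40% as compared to a maximum regression rate of 10% in the observation arm". That pair is attached to the original sample size, which Section 10.1 gives as 50 per arm. Section 10.3 then says that the revised 35 per arm was fixed by the date on which accrual was expected to close. It gives no new effect size and no new power.

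On power, Section 1.2 says "The effect of this sample size change on statistical power is discussed in" Section 10.0. The only power information in Section 10 is the last column of Table 10-A in Section 10.6.2, which is labelled as beta, or 1 minus power. Its final row reads "2 (Final) 70 (100%) 1.955 (0.025) 1.955 (0.025) 0.025 0.100": 70 participants, final bound 1.955, overall alpha 0.025, overall beta 0.100. The Version 8.0 summary of changes says "Table 10-A was updated to reflect the updated sample size" and lists the beta column among the items updated, so the entry is current text.

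On alpha, Section 10.6.2 describes group sequential methods "preserving the overall one-sided significance level of 0.025 for each comparison". Section 10.7 says of the same comparison that "the proportions will be compared across sites using stratified Mantel-Haenszel-Cochran tests at the one-sided 0.05 alpha level".

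**The concern.** A reader who follows Section 1.2 to Section 10 finds 90% power at 70 participants. The one alternative available to attach to that figure is 40% vs 10%. The sample size fell by 30% (50 to 35 per arm) and was set by the calendar, so there is no reason to expect it to land on 90% for an effect chosen earlier. If it does not, the plan understates the chance of missing its own minimum effect of interest, and a non-significant result would be read as stronger evidence against 5FU than the design supports. The two alpha levels add to the problem, because beta has no meaning until the alpha it goes with is settled.

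**Working it through.** **Inputs.** Rates 0.40 and 0.10 and 35 per arm (Section 10.3). Interim at 50% information, interim futility bound 0.258, interim efficacy bound 2.963, final bound 1.955, overall alpha 0.025, overall beta 0.100 (Table 10-A). One-sided 0.05 (Section 10.7).

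**Model.** (Z1, Z2) is bivariate normal with means θ√0.5 and θ, unit variances and correlation √0.5. With the futility bound binding,

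power = P(Z1 ≥ 2.963) + P(0.258 < Z1 < 2.963 and Z2 ≥ 1.955).

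**Step 1: reproduce the table.**
- At θ = 0 the formula gives 0.0250, the tabulated overall alpha.
- Setting power to 0.90 gives θ = 3.268. The interim beta is then Φ(0.258 − 3.268 × 0.7071) = Φ(−2.053) = 0.020, as tabulated.

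The table is therefore self-consistent, and its beta of 0.100 corresponds to a drift of 3.268.

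**Step 2: drift at 40% vs 10%, 35 per arm.**
- Unpooled: 0.30 / √[(0.24 + 0.09)/35] = 0.30 / 0.0971 = 3.090
- Pooled (mean rate 0.25): 0.30 / √[2 × 0.25 × 0.75/35] = 0.30 / 0.1035 = 2.898
- Arcsine: 3.037

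All three fall below 3.268.

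**Step 3: power with the table's bounds.**

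| Drift | Efficacy at interim | Stop for futility | Efficacy at final | Total power |
|---|---|---|---|---|
| 3.090 (unpooled) | 0.218 | 0.027 | 0.647 | 0.866 |
| 3.037 (arcsine) | 0.207 | 0.029 | 0.647 | 0.854 |
| 2.898 (pooled) | 0.180 | 0.037 | 0.640 | 0.820 |

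If futility is non-binding, these become 0.872, 0.861 and 0.828.

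**Step 4: exact check.** Enumerating all binomial outcomes of the two-stage design with the pooled Z statistic gives 0.848 for an 18/17 interim split and 0.847 for 17/18. Beta is 1 − 0.848 = 0.152. Against 0.90 the shortfall is about 5 points. Across all methods it runs from 2.8 (0.900 − 0.872) to 8.0 (0.900 − 0.820).

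**Step 5: what would give beta 0.100.**
- *Sample size at 40% vs 10%.* A drift of 3.268 needs n = 3.268² × 0.33/0.09 = 39.2 (unpooled) or 3.268² × 0.375/0.09 = 44.5 (pooled). Exact power is 0.897 at 40 per arm and 0.905 at 41.
- *5FU rate at 35 per arm with observation at 10%.* 0.429 exact (0.419 to 0.449 by normal approximation).
- *Observation rate at 35 per arm with 5FU at 40%.* 0.083 exact (0.069 to 0.088 by normal approximation).
- *Alpha.* At one-sided 0.05 with a single look, Φ[(0.30 − 1.645 × 0.1035)/0.0971] = Φ(1.336) = 0.909. With two looks and bounds that spend 0.05 (2.538 and 1.662), exact power is 0.905 to 0.916, depending on how futility is handled.

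**Step 6: effect of the cut.** The same bounds applied to 50 per arm at 40% vs 10% give exact power 0.951. This uses the Version 8.0 bounds at both sizes. The superseded table is not in the document.

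**The case against.** No sentence claims 90% power at 40% vs 10% with 35 per arm. Section 10.3 ties those rates to the original size, and Table 10-A names no alternative, so strictly the fault is an unstated alternative. This is fair. Beta may simply have been an input to the boundary calculation, which would explain why the bounds and the interim beta of 0.020 fit a single drift so closely; that is an inference. But the summary of changes says the beta column was updated for the new size, and Section 1.2 points to Section 10 for power, so 0.100 will be read as power at 70 participants. An unstated alternative leaves that figure unsupported.

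The result also depends on the rates. Section 10.3 presents 40% as a floor and 10% as a ceiling, so 85% is power at the least favourable pair. Section 1.2 cites a study that "observed regression in one out of 25 participants randomized to placebo". At that 4% rate, against 40%, exact power is 0.98. This stands, but a design's power is conventionally quoted at its stated minimum effect.

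Section 10.7's one-sided 0.05 gives about 91%, so beta 0.100 could be said to match that section. But the bounds printed in the same table spend 0.025, and a beta computed at 0.05 cannot be paired with them.

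Site stratification does not rescue the figure. A single-look simulation of the stratified test with 1 to 18 equal sites also gives about 0.85.

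Last, enrolment closed on 1 July 2023, so no sample-size decision depends on this. That limits the consequence to reporting and interpretation.

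**Conclusion.** The concern holds. With Table 10-A's own bounds and alpha, 35 per arm and 40% vs 10%, power is about 85% (exact 0.847 to 0.848; 0.820 to 0.872 across approximations), not 90%. At the planned minimum effect the chance of a miss is about 15 in 100 (13 to 18 across methods), where the table shows 10 in 100. Under the same bounds, going from 50 to 35 per arm costs about 10 points (0.951 to 0.848), and the text does not show this.

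This assumes 1:1 allocation, an interim at half the information, and that 40% and 10% are intent-to-treat rates in which dropouts already count as failures, as Section 10.7 counts them. Type I error under the tabulated bounds, the bounds themselves, the sample size and the conduct of the trial are not affected. The stated power should be corrected because it governs how a non-significant result is read.

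**What to change.** 1. Change the level for the primary comparison in Section 10.7 from one-sided 0.05 to the one-sided 0.025 that Section 10.6.2 and the Table 10-A bounds already use. If the sponsor intends 0.05 instead, the bounds and the alpha column would have to be recomputed.
2. State the alternative behind beta in Section 10.3 and in a footnote to Table 10-A. Either:
   - replace 0.100 and add: *At a complete response rate of 40% with 5FU and 10% with observation, 35 participants per arm and the bounds shown give an overall beta of about 0.15 (power about 85%).* The interim beta should be restated at the same alternative (0.027 to 0.037 by the normal approximations above); or
   - keep 0.020 and 0.100 and name the effect that yields them: about 43% vs 10%, or 40% vs about 8%.

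The first option is preferable because it keeps the effect that the trial was designed to detect. The cost is two or three sentences and a table entry. The stated power becomes less favourable. No participants are added and, at 0.025, no stopping bound changes.
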